8.1 Endpoints

(i) Decisional Conflict scale mean score at **month 0**

8.2 Hypotheses

Participants in the MyChoice intervention group will report, on average, decisional conflict scores lower than participants in the control group.

H_0 : The mean DCSs of the MyChoice and SOC arms are equal.

H_1 : The mean DCSs of the MyChoice and SOC arms are not equal (2-tailed). For 1-tailed test, you would use an H_1 of the mean DCS in the MyChoice arm is lower than the mean DSC in the SOC arm.

8.3 Cohort and Study Arm

Secondary outcomes will be assessed only among participants randomized to both the MyChoice Intervention and SOC arm using ITT.

8.4 Measures

(a) The DCS scale contains 16 items rated on a 5-point scale. The scale questions may be found on the Decisional Conflict Scale REDCap instrument (**Appendix C**). Each scale item is rated from 1 to 5 ("strongly agree" to "strongly disagree"). Each of the questions include a non-response option (999), that will be set to missing for analysis. DCS scores will be computed based on women's responses to statements, where higher scores

indicate greater decisional conflict, while lower scores indicate diminished conflict and heightened certainty in decision-making. DCS scores are computed as the mean rating across items multiplied by 25 (theoretical range: 0 to 100). The scale will be administered at the month 0 visit following completion of study counselling.

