5.15.1 Precision calculations for continuous outcomes

For continuous measures, such as mean acceptability, appropriateness, and feasibility scores, or mean decisional conflict score, we used the t-distribution to estimate the level of precision we can expect to achieve given our various sample sizes and an expected 10% loss to follow-up over the course of the study. Table 6 shows the precision we can expect for estimates of 95% confidence intervals for mean acceptability, appropriateness, or feasibility at baseline

and at follow-up. If we assume a common standard deviation of 0.9, we can expect a margin of error of ± 0.256 points at baseline and ± 0.270 points at follow-up on a 4-point scale. Likewise, Table 7 shows estimates of precision for 95% confidence intervals around mean decisional conflict score (DCS), except means will be estimated overall and by each arm. Here, if we assume a common standard deviation of 13.26, we can expect the margin of error for the 95% CI around the means to range from ± 2.6 (pooled at baseline) to ± 4.0 (by arm at follow-up) points on a 100-point scale.

For primary outcomes, mean AIM, IAM, and FIM, assumed SD=0.9 for all measures based on Lavoie et al. Mean AIM, IAM, and FIM calculated among intervention arm only.
Table 6. Expected precision for mean acceptability, appropriateness, or feasibility score among intervention arm

Precision Estimate for 95% CI of Mean*

Baseline (n=50)	± 0.256
Follow-up (n=45) [†]	± 0.270

*Assume SD=0.9 for mean acceptability, appropriateness, and feasibility scores (4-point scale); precision estimates for 95% confidence intervals obtained using t-distribution.

†Assume 10% loss to follow-up by the end of study

For secondary outcome, mean DCS, assumed SD=13.26 for each arm based on Vleminck et al. Mean DCS will be calculated and compared by arm.
Table 7. Expected precision for mean decisional conflict score, overall and by study arm

Precision Estimate for 95% CI of Mean*

Overall	Precision Estimate for 95% CI of Mean*
Baseline (n=100)	± 2.631
Follow-up (n=90) [†]	± 2.777
By arm	
Baseline (n=50)	± 3.768
Follow-up (n=45) [†]	± 3.984

*Assume SD=13.26 for mean decisional conflict score (100-point scale); precision estimates for 95% confidence intervals obtained using t-distribution.

†Assume 10% loss to follow-up by the end of study

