8.5 Analysis

- (i) **Item-Level Summary:** We will describe the responses for each of the 16-items on the Decisional Conflict Scale (DCS) at **month 0**. Descriptive statistics will include counts, percentages, and graphical summaries, as appropriate.
- (ii) **Scale-Level Summary:** For each participant, in each study arm, we will calculate the mean of their completed DCS at **Month 0** and multiply that result by 25 to produce a standardized summary score ranging from 0 to 100, in accordance with the established scoring procedures. Only participants with at least one completed DCS item will be included in the analysis. For each study arm, we will calculate the mean of participants' individual summary scores (mean of means), the SD, and the 95% CI using the common variance.
- (iii) **Between-Group Comparisons:** We will compare the mean DCS scores between the intervention (MyChoice) and SOC arms using the Welch's t-test (assuming unequal variance). We will also report the absolute difference in mean scores between arms (SOC as the referent), along with the associated 95% CI using the pooled variance assumption.
- (iv) **Missing Data:** If more than >10% of participants in either randomization group are unevaluable, multiple imputation (MI) may be applied as described in section 6.7.
- (v) **Adjustment for Imbalances:** If key demographic variables or baseline characteristics related to decisional conflict differ substantively by study arm, we will use AIPW to adjust for these differences, as described in section 6.6

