Appendix C: Secondary Outcome Questionnaire (DCS)

Instructions: Now, please think about the decision you made to use a HIV prevention method as a part of this study. Please indicate how you feel about each of these statements by indicating a number from 1 (strongly agree) to 5 (strongly disagree).

	Strongly Agree	Agree	Neither Agree nor Disagree	Disagree	Strongly Disagree	No Response
I know which options are available to me.						
I know the benefits of each option.						
I know the risks and side effects of each option.						
I am clear about which benefits matter most to me.						
I am clear about which risk and side effects matter most to me.						

I am clear about
which is more
important to me
(the benefits or
the risks and side
effects).

I have enough
support from
others to make a
choice.

I am choosing
without pressure
from others.

I have enough
advice to make a
choice.

I am clear about
the best choice for
me.

I feel sure about
what to choose.
This decision is
easy for me to
make.

I feel I have made
an informed
choice.

My decision
shows what is
important to me.

I expect to stick
with my decision.

I am satisfied with
my decision.

References

2. O'Connor AM. Validation of a decisional conflict scale. *Med Decis Making.* 1995;15(1):25-30. doi:10.1177/0272989X9501500105
5. Sun Q. *Predicting Downstream Effects of High Decisional Conflict: Meta-Analyses of the Decisional Conflict Scale.* 2005.

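### The Decisional Conflict Scale scoring rule in the SAP gives 25–125 on items coded 1–5, not the stated 0–100; a step subtracting 1 from the ratings is missing

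*SAP*

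**What the plan says.** The SAP's only secondary endpoint is the month 0 DCS mean (section 8.1: "Decisional Conflict scale mean score at" month 0). Four statements in the SAP fix how it is scored.

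- Item codes, section 8.4: "Each scale item is rated from 1 to 5", running from strongly agree to strongly disagree. The questionnaire in Appendix C agrees: women respond by "indicating a number from 1 (strongly agree) to 5 (strongly disagree".
- Handling before scoring, section 8.4: "Each of the questions include a non-response option (999), that will be set to missing for analysis". No other DCS data step is given.
- Formula and range, section 8.4: "DCS scores are computed as the mean rating across items multiplied by 25 (theoretical range: 0 to 100".
- Formula and range again, section 8.5(ii): take each participant's mean and "multiply that result by 25 to produce a standardized summary score ranging from 0 to 100, in accordance with the established scoring procedures".

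Section 8.5(ii) then reports, for each arm, the mean of the "individual summary scores (mean of means), the SD, and the 95% CI using the common variance".

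Protocol sections 5.9.2 and 5.16.2 give the same multiplier and a 100-point scale, but say only that items are on a 5-point scale; they give no numeric codes. The conflict therefore arises in the SAP, where the 1–5 codes are specified.

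**The concern.** A multiplier of 25 turns a mean rating into a 0–100 score only if the mean itself runs from 0 to 4. With ratings from 1 to 5, the stated codes, formula and range cannot all be true. A programmer who applies the formula to the data as collected will report DCS levels that are too high in both arms.

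The absolute levels matter because the arm means with their 95% CIs are the reported secondary result, and the pilot is meant to inform the design of an efficacy trial. The protocol also plans an exploratory split at 25 out of 100, which has its intended meaning only on a true 0–100 scale. The error could pass unnoticed, because most of the inflated scores still fall between 0 and 100.

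**Working it through.** **Inputs.** 16 items, coded 1 (strongly agree) to 5 (strongly disagree) (SAP 8.4, Appendix C). Score = mean × 25, stated range 0–100 (SAP 8.4, 8.5(ii)). Assumed SD 13.26 and expected by-arm 95% CI margin ±3.768 at n = 50 (Protocol 5.15.1 and Table 7). Low-conflict cut-off 25 out of 100 (Protocol 5.9.2 and 5.16.2).

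**Step 1: try to reproduce the stated range.**

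| Item codes | Formula | Minimum | Maximum |
|---|---|---|---|
| 1–5 (as written) | mean × 25 | 1 × 25 = 25 | 5 × 25 = 125 |
| 0–4 | mean × 25 | 0 × 25 = 0 | 4 × 25 = 100 |
| 1–5 | (mean − 1) × 25 | 0 × 25 = 0 | 4 × 25 = 100 |
| 1–5 | mean × 20 | 1 × 20 = 20 | 5 × 20 = 100 |

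Only the second and third rows give 0–100. They are the same score, and neither is written in the SAP or the protocol.

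**Step 2: look for a recode elsewhere.** The reverse-coding in SAP 7.5 covers only the acceptability, appropriateness and feasibility scales, and leaves them on 1–5. The DCS needs no reversal: its items in Appendix C are worded so that agreement means less conflict, and 1 is strongly agree. The direction is right; only the origin is wrong.

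**Step 3: size of the shift.** For a participant with mean rating m over the items she answered, 25m − 25(m − 1) = 25. The shift is exactly +25 however many items are answered.

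For scale, first reproduce the protocol's margin: t(0.975, 49) × 13.26/√50 = 2.0096 × 1.8752 = 3.768, which matches Table 7. Then 25/3.768 = 6.6 margins, and 25/13.26 = 1.89 SDs. These ratios describe how far the reported levels move. They are not a bias in the treatment effect.

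**Step 4: what does not change.** Adding 25 to every score in both arms leaves the mean difference at (a + 25) − (b + 25) = a − b, and leaves both variances as they were. The confidence interval for the difference, Welch's t, its degrees of freedom and p-value, the protocol's 8-point hypothesis and the Table 7 precision all stand.

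**Step 5: would a range check catch it?** With all 16 items answered, totals run from 16 to 80, giving 65 attainable scores. The written rule exceeds 100 only if total/16 × 25 > 100, that is, total ≥ 65. That is 16 of the 65 scores; the lowest is 65/16 × 25 = 101.6, where the recoded value is 76.6. The other 49 lie between 25 and 100 and pass an upper-limit check.

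**Step 6: the cut-off, if it were used.**

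| Responses | As written | Recoded |
|---|---|---|
| All strongly agree | 25 | 0 |
| 15 strongly agree, 1 agree | 17/16 × 25 = 26.6 | 1.6 |
| All agree | 50 | 25 |
| All neutral | 75 | 50 |

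A score of 25 or below requires a total of 16 as written (1 of 65 attainable scores), and a total of 32 or less after recoding (17 of 65). These count possible scores, not women.

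**The case against.** The strongest reply is that nobody could mistake the intended score. Both documents repeat the 100-point scale, the protocol defers to published methods, and SAP 8.5(ii) appeals to established procedures. An analyst who respects the stated range will notice that 1–5 codes do not fit it and will subtract 1. The comparison between arms is also immune to the shift, and Aim 2 is about plausible intervention effects rather than absolute levels. Finally, the low-conflict cut-off is exploratory and appears only in the protocol, and a lower-limit check would show that no score ever falls below 25.

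Much of this stands. The target scale is clear, the treatment comparison is unaffected, the cut-off consequence is conditional, and an alert analyst could spot the empty range below 25.

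It does not remove the fault. The SAP gives an explicit formula that, applied to the coding it specifies, yields wrong values, and the reference to established procedures does not supply the missing step. The same SAP writes out the recode for the three primary scales in full, so silence for the DCS can reasonably be read as meaning that no recode is needed. The arm means and their intervals are planned outputs, and they would be wrong.

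**Conclusion.** The point holds. The DCS codes, formula and range in the SAP are mutually inconsistent: as written, the rule gives 25–125. Followed literally, every score, both arm means and the limits of their 95% CIs are 25 points too high. The between-arm difference and everything built on it are correct either way.

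The conclusion rests on two things: that the data are held as the 1–5 codes shown in Appendix C, and that the stated 0–100 range is the intended scale, as both documents say throughout. How far the proportion of women classed as low conflict would fall cannot be worked out from the documents, because it depends on how women actually respond. The fault should be corrected before the outcome analysis. It does not threaten the trial's comparison.

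**What to change.** In SAP section 8.4, replace the scoring sentence with one stating that non-missing items are recoded from 1–5 to 0–4 before averaging, so that

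DCS = (mean of non-missing 1–5 ratings − 1) × 25, range 0 to 100.

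Refer to that definition from section 8.5(ii), and apply any cut-off of 25 only to the recoded score. In the program, add the subtraction and check that all strongly agree scores 0 and all strongly disagree scores 100.

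The cost is one sentence in the SAP and one line of scoring code. Data collection does not change. No protocol amendment is needed: the protocol gives no item codes that conflict with this, and its section 5.16 leaves detailed analysis to the SAP.

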8.5 Analysis

- (i) **Item-Level Summary:** We will describe the responses for each of the 16-items on the Decisional Conflict Scale (DCS) at **month 0**. Descriptive statistics will include counts, percentages, and graphical summaries, as appropriate.
- (ii) **Scale-Level Summary:** For each participant, in each study arm, we will calculate the mean of their completed DCS at **Month 0** and multiply that result by 25 to produce a standardized summary score ranging from 0 to 100, in accordance with the established scoring procedures. Only participants with at least one completed DCS item will be included in the analysis. For each study arm, we will calculate the mean of participants' individual summary scores (mean of means), the SD, and the 95% CI using the common variance.
- (iii) **Between-Group Comparisons:** We will compare the mean DCS scores between the intervention (MyChoice) and SOC arms using the Welch's t-test (assuming unequal variance). We will also report the absolute difference in mean scores between arms (SOC as the referent), along with the associated 95% CI using the pooled variance assumption.
- (iv) **Missing Data:** If more than >10% of participants in either randomization group are unevaluable, multiple imputation (MI) may be applied as described in section 6.7.
- (v) **Adjustment for Imbalances:** If key demographic variables or baseline characteristics related to decisional conflict differ substantively by study arm, we will use AIPW to adjust for these differences, as described in section 6.6

Appendix A: Visits and Visit Windows

Study visit schedule

Procedure	Screening	Enrollment Visit	Follow-up visits		
			1 mo. (-/+ 15 days)	2 mo. (+/- 15 days)	3 mo. (+/- 15 days)
Study introduction	X				
Eligibility assessment	X				
Informed consent		X			
SDM counseling (intervention)		X			
Questionnaires		X	X	X	X
PrEP assisted referral		X			
Qualitative interviews			X		X
Adherence measurement (PrEP adopters only)					
Pill count/self-report			X	X	X
DBS				X	

Appendix B: Primary Outcome Questionnaires (AIM, IAM, FIM)

The Acceptability of Intervention Measure (AIM), Intervention Appropriateness Measure (IAM), and Feasibility of Intervention Measure (FIM) was adapted from the Weiner Psychometric assessment of three newly developed implementation outcome measures. (2017)¹ Response options were switched to from Completely Disagree to Completely Agree to Completely Agree to Completely Disagree to mimic the response options from other scale that were used throughout the study.

Instructions: I'd like to know what you think about the study you've been participating in to support your use of an HIV prevention method of your choice. Remember, this program consists of PrEP, female, and male condoms. Please indicate how you feel about each of these statements by indicating a number from 1 (completely agree) to 5 (completely disagree).

Acceptability of Intervention

	Completely Agree	Agree	Neither Agree nor disagree	Disagree	Completely Disagree
The shared-decision counseling study meets my approval					
The shared-decision counseling study is appealing to me.					
I like the shared-decision counseling I received.					
I welcome the shared-decision counseling.					

Instructions: I'd like to know what you think about the study you've been participating in to support your use of an HIV prevention method of your choice. Remember, this program consists of PrEP, female, and male condoms. Please indicate how you feel about each of these statements by indicating a number from 1 (completely agree) to 5 (completely disagree).

Intervention Appropriateness Measure

	Completely Agree	Agree	Neither Agree nor disagree	Disagree	Completely Disagree
The shared-decision counseling seems fitting.					
The shared-decision counseling seems suitable.					
The shared-decision counseling seems applicable.					
The shared-decision counseling seems like a good match.					

Instructions: Now I'd like to ask you about how much you agree with the following 4 statements regarding the decision counseling you took part in. Please indicate how you feel about each of these statements by indicating a number from 1 (Completely agree) to 5 (completely disagree).

Feasibility of Intervention Measure

	Completely Agree	Agree	Neither Agree nor Disagree	Disagree	Completely Disagree
The shared-decision counseling seems implementable.					
The shared-decision counseling					

seems possible.
The shared-decision counseling seems doable.
The shared-decision counseling seems easy to use.

Appendix C: Secondary Outcome Questionnaire (DCS)

Instructions: Now, please think about the decision you made to use a HIV prevention method as a part of this study. Please indicate how you feel about each of these statements by indicating a number from 1 (strongly agree) to 5 (strongly disagree).

	Strongly Agree	Agree	Neither Agree nor Disagree	Disagree	Strongly Disagree	No Response
I know which options are available to me.						
I know the benefits of each option.						
I know the risks and side effects of each option.						
I am clear about which benefits matter most to me.						
I am clear about which risk and side effects matter most to me.						

I am clear about
which is more
important to me
(the benefits or
the risks and side
effects).

I have enough
support from
others to make a
choice.

I am choosing
without pressure
from others.

I have enough
advice to make a
choice.

I am clear about
the best choice for
me.

I feel sure about
what to choose.
This decision is
easy for me to
make.

I feel I have made
an informed
choice.

My decision
shows what is
important to me.

I expect to stick
with my decision.

I am satisfied with
my decision.

References

2. O'Connor AM. Validation of a decisional conflict scale. *Med Decis Making.* 1995;15(1):25-30. doi:10.1177/0272989X9501500105
5. Sun Q. *Predicting Downstream Effects of High Decisional Conflict: Meta-Analyses of the Decisional Conflict Scale.* 2005.
